**Objective 2. To study the results of applying organ-substituting technologies in the treatment of sepsis.**

**Subtask 2.1.** Assessment of the recovery of organ function in the application of extracorporeal hemocorrection in septic patients.

**Subtask 2.2.** Evaluation of the normalization of the organism immune response and restoration of organ function when using the extracorporeal cytokine adsorber in septic patients.

**Subtask 2.3.** Evaluation of the normalization of the organism immune response and restoration of organ function when using the extracorporeal hemoperfusion cartridge.

## 3. Scientific novelty and significance of the program

According to statistics, CHF is an increasingly widespread condition in most countries of the world. In the general population within adults, CHF is revealed annually in 1-2% of the population [1]. With increasing age, the incidence of CHF is increasing exponentially. The incidence of CHF reveals its multiple increase in each subsequent age group: in 25-34 years old - 0.02 per 1000 population, in 55-64 - 3.0-4.0 per 1000, 75-84 years - 13.0- 14.0 per 1000 population [2-5]. The constant increase in the number of patients with CHF is associated with both an increase in the life expectancy of patients and a decrease in mortality among patients with a complicated course of acute myocardial infarction, heart defects, etc. The most common causes of CHF are arterial

hypertension, coronary heart disease and myocardial infarction. The gold standard for treating patients with terminal heart failure, tolerance to drug therapy is heart transplantation.

In 2012 the JSC “National Research Center for Cardiac Surgery” developed the heart transplantation program in Kazakhstan. Considering the geographical features of our country (donor hearts are transported from regions remote from the Center > 1000 km.), remote delivery and heart preservation has been developed using an organ preservation system. The Center has been performed 81 heart transplants for 8 years. The survival rate by 12 months was 80%. According to data, for 2018, more than 200 people need heart transplants every year in Kazakhstan.

The lack of donor organs remains the most important factor hindering the development of lung and heart transplants throughout the world and in our country.

Extracorporeal membrane oxygenation (ECMO) is a procedure for prolonged cardiopulmonary bypass and oxygenation of the blood outside the body, used in patients with acutely frisky and potentially reversible respiratory and / or heart failure, whose treatment is not amenable to the maximum standard therapy. In 2011, the JSC “National Research Center for Cardiac Surgery” launched a program to provide ECMO in Kazakhstan, and in 2016 the Center entered to the World Register ELSO (Extracorporeal Life Support Organization) [6-14].

Sepsis, septic shock and SIRS are life-threatening conditions associated with an overreacting immune response. The deregulated response can lead to multiple organ dysfunction [15-21].

While sepsis and septic shock have an infectious origin, SIRS may also have non-infectious triggers such as cardiac surgery using the Cardiopulmonary Bypass (CPB), ex vivo heart/lung perfusion device, ECMO, and Mechanical circulatory Support. This is of particular interest for this report. SIRS, sepsis and septic shock have a mortality of an estimated 7, 16 and 40% respectively [22-30]. The new 2016 Sepsis-3 definition has two grades: sepsis and septic shock [31-34]. The previous sepsis definitions published in 1992 emphasized on the role of systemic inflammatory response syndrome (SIRS) as a key element of the sepsis definition.

However, evidence showed that SIRS criteria are non-specific and insensitive as predictor for sepsis related mortality, thus are not included in the most recent international sepsis definitions. The members of the Sepsis-3 taskforce suggested that sepsis should be considered in the event of an infectious process associated with an increase in SOFA score of two points or more. Patients with septic shock would be clinically identified by a vasopressor requirement to maintain a mean arterial pressure of 65 mmHg or greater, and serum lactate level greater than 2 mmol/l (>18 mg/dl) in the absence of hypovolemia. SIRS patients identified by fulfilling two or more of the four SIRS criteria. The two main therapeutic priorities include early identification of a potential infectious origin and hemodynamic stabilization of the patient. Other than the control of the primary site of infection, there is no causal treatment for sepsis, septic shock or SIRS [35-39].

In order to improve the results of ECMO and septic patients, various techniques used to reduce the systemic inflammatory response syndrome, immunocorrection, and others. Today, there are many ways to prevent the development of a systemic inflammatory response by removing leukocytes from the bloodstream by inserting a filter with a special screen into the perfusion circuit to remove leukocytes and prevent them from entering the systemic circulation [9].

The most effective method is the hemoabsorption, intended for additional therapy of patients with elevated levels of cytokines in the context of systemic inflammatory response syndrome. In-patient with acute respiratory distress syndrome and cardiogenic septic shock on the background of extracorporeal membrane oxygenation (ECMO) and mechanical support of the left ventricle, additionally installed a system for veno-venous hemofiltration, a system designed to eliminate a wide range of inflammatory mediators also various proteins and metabolites [40-46].

There are some new data showing that the use of extracorporeal cytokine adsorber and hemoperfusion cartridge for a long time cardiopulmonary shunting ( $> 120$  minutes) may be useful in preventing CVS and reducing cytokine levels in patients undergoing heart surgery [47-53].

In this study, will be developed methods to restore the function of affected organs after implantation of ECMO and patients with sepsis in combination with extracorporeal hemocorrection, which will improve the results of surgical treatment of patients with end-cardiac and respiratory failure.

New methods developed to restore the function of affected organs after implantation of mechanical support devices and patients with sepsis will be a great importance both for Kazakhstan and for countries with similar category of patients, which will improve the efficiency of surgical treatment and reduce the level of complications and mortality.

Clinical research data will form the basis of practical protocols for extracorporeal membrane oxygenation (ECMO) and patients with sepsis, which will improve organ repair, reduce postoperative complications, improve quality of life and reduce mortality after surgery.

#### **4. Research methods and ethical issues**

Patients before implantation of ECMO and/or patients with sepsis will be enrolled in the study after giving a written, signed informed consent.

The participants will be randomized into 3 groups:

- **Intervention group #1** a cytokine adsorber will be used (30 patients): patients on ECMO – subgroup A; septic patients – subgroup B.
- **Intervention group #2** an extracorporeal hemoperfusion cartridge will be used (30 patients): patients on ECMO – subgroup C, septic patients – subgroup D.

- **Control group #3** without using extracorporeal adsorber (30 patients): patients on ECMO subgroup - E, septic patients - subgroup F.

The investigators will collect demographic, clinical and laboratory data about patients before, during and after the operation

The incidence of early cellular or humoral rejection, length of ventilation, ICU and hospital stay, the use of vasopressors and inotropes in the perioperative period and incidence of perioperative complications and survival will be documented.

The level of cytokines (IL-1, IL-6, IL-8, IL-10, tumor necrosis factor-alfa) and complements before, during and after the use of ECMO, patients with sepsis will be determined if the investigators find relevant difference between the two groups in clinical variables.

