### Study Design

Study Type: Interventional (Clinical Trial)

Estimated Enrollment: 90 Participants

Allocation: randomized

Interventional Model: Parallel assignment

Masking: None (Open Label)

Experimental (subgroups)	Intervention / treatment (device)
Cytokine adsorber filter will be installed into the (hemodialysis or cardiopulmonary bypass (CPB) (15 patients on ECMO)	Cytokine adsorber is a biocompatible, high adsorptive polymer indicated in conditions where cytokine levels are extremely elevated.
Cytokine adsorber filter will be installed into the (hemodialysis or cardiopulmonary bypass (CPB) (15 patients with sepsis)	Cytokine adsorber is a biocompatible, high adsorptive polymer indicated in conditions where cytokine levels are extremely elevated.
Extracorporeal hemoperfusion cartridge will be installed into the (hemodialysis or cardiopulmonary bypass (CPB) (15 patients on ECMO)	Extracorporeal hemoperfusion cartridge is a biocompatible, high adsorptive polymer indicated in conditions where cytokine levels are extremely elevated.
Extracorporeal hemoperfusion cartridge will be installed into the (hemodialysis or cardiopulmonary bypass (CPB) (15 patients with sepsis)	Extracorporeal hemoperfusion cartridge is a biocompatible, high adsorptive polymer indicated in conditions where cytokine levels are extremely elevated.
Control (subgroups)	
No filter will be installed into the ECMO in	

this study group (15 patients)	
No filter will be installed into the patient with sepsis (15 patients)	

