## Outcome Measures

### Primary Outcome Measures

#### *ECMO patients*

1. Difference of Cytokine response [ Time Frame: 6-24 hours ]

Level of pro- and anti-inflammatory cytokines (IL-1, IL-6, IL-8, IL-10, tumor necrosis factor-alfa) before initiation of ECMO, 2 hours after initiation ECMO support, at explantation of ECMO support, 6-12-24 hours after explantation of ECMO support.

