#### Secondary outcomes

1. Ventilator free days (VFD) [Time Frame: 30 days]

Ventilator free days (VFD) in the first 30 days after randomization, where invasive mechanical ventilation (IMV), non-invasive ventilation (NIV) and ECMO are defined as ventilator days. VFD=0, if the patient dies in the first 30 days after randomization

2. Time to extubation from ventilation and explantation from ECMO [ Time Frame: 30 days ]

Time to extubation from ventilation and explantation from ECMO. Death under ventilation and/or ECMO will be analyzed as a competing event. The time will be censored at the time of last visit for surviving patients under ventilation and/or ECMO.

3. Difference of d-dimers [Time Frame: 24, 48, 72 hours]

Comparison to enrollment or between 3 groups at 24, 48, 72 h

4. Difference of Serum lactate [Time Frame: 24, 48, 72 hours]

Comparison to enrollment or between 3 groups at 24, 48, 72 h

5. SOFA-Score [Time Frame: 24, 48, 72 hours]

Sequential Organ Failure Assessment Score at 24, 48, 72 h (values from 6 to 24, where the higher values explain higher disease severity)

6. Serious adverse device effects [Time Frame: 30 days]

Serious complications or malfunctions related to the CytoSorb device

7. Adverse event of special interest: air in the ECMO system [Time Frame: 30 days]

- Unintended air in the ECMO system during operation of the device
- 8. Adverse event of special interest: blood-clotting in the ECMO system [Time Frame: 30 days]
  - Unintended blood-clotting in the ECMO system during operation of the device
- 9. Adverse event of special interest: bleeding complications [Time Frame: 30 days]
  - Major bleeding events

*Patient with septic shock*

- 1. Difference of Cytokine response [ Time Frame: 24-48 hours of septic shock ]
  - Cytokine response: Level of procalcitonin, Level of C-reactive protein, Level of interleukin-1, Level of interleukin-6, Level of interleukin-8, Level of interleukin-10, Level of Tumor Necrosis Factor-  $\alpha$  at 24, 48 hours.

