**Secondary Outcome Measures:**

- 1. Inflammatory reaction [Time Frame: 6 - 24 hours]
  - Level of C reactive protein (CRP), white blood cells and procalcitonin immediately after induction of anesthesia, before initiation of adsorber, 2 hours after initiation of adsorber, at termination of adsorber, 6-12-24 hours after wean of adsorber.
- 2. Difference of serum interleukin-6 level [Time Frame: 48, 72 hours]
  - Comparison to enrollment or between 3 groups at 48, 72 h
- 3. Difference of serum interleukin-1 $\beta$  level [Time Frame: 24, 48, 72 hours]
  - Comparison to enrollment or between 3 groups at 24, 48, 72 h
- 4. Difference of serum interleukin-10 level [Time Frame: 24, 48, 72 hours]
  - Comparison to enrollment or between 3 groups at 24, 48, 72 h
- 5. Difference of serum procalcitonin level [Time Frame: 24, 48, 72 hours]
  - Comparison to enrollment or between 3 groups at 24, 48, 72 h

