### Statistical studies

1) Statistical data processing

2) Comparison and analysis of source data

After data receiving, statistical analysis will be performed using SPSS Statistics software version 22. For quantitative data, the Mann-Whitney Yu non-parametric test and parametric t-test will be performed, and Fisher's non-parametric exact test and  $\chi^2$  parametric test will be performed for qualitative studies. Also, a logistic regression for categorical outcomes and a survival analysis (non-parametric Kaplan-Meier and parametric Cox regression) will be performed.

**Ages:**18 Years and older

**Sex:** All

**Accepts healthy volunteers:** No

Groups	Inclusion criteria	Exclusion Criteria:
ICU patients with ECMO	

• Hemodynamic support with vasopressors

• Procalcitonin level <math>\geq 1</math> ng/ml

• Invasive hemodynamic monitoring

• Written informed content

	

• age <math>< 18</math> years

• acute liver or kidney failure straight before transplantation

• the patient declines participating in the study

ICU patients with septic shock of medical origin	

• Signs of hypoperfusion: serum lactate <math>>2</math> mmol/L, low central venous oxygen saturation (ScvO2) (<math><70\%</math>) or high ScvO2 (<math>>85\%</math>), metabolic acidosis, oligo-anuria,

	

• Patients under 18 years

• Pregnancy (bHCG test positivity)

• Surgical intervention in context with the septic insult

	
high venous-to-arterial CO2-gap (dCO2 >6 mm Hg)
 
 
• Hemodynamic support with vasopressors
 
• Procalcitonin level <math>\geq</math> 1 ng/ml
 
• Invasive hemodynamic monitoring
 
• Written informed content
 
	
New York Heart Association IV heart failure
 
 
• Acute coronary syndrome
 
• Acute haematological malignancies
 
• Immunosuppression, systemic steroid therapy (>10mg prednisolon/day)
 
• Human immunodeficiency virus infection (HIV) and active AIDS
 
• Patients with donated organs
 
• Thrombocytopenia (<20.000/ml)
 
• More than 10%-of body surface area with third degree burn
 

--	---	--

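### The methods section makes the cytokine assays conditional on an undefined clinical difference, while the outcome lists require them outright, so the ECMO primary outcome could go unmeasured

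*Combined protocol and SAP*

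**What the plan says.** Section 4 (Research methods and ethical issues) states that "The participants will be randomized into 3 groups": cytokine adsorber, hemoperfusion cartridge and control, with 30 patients each. Later in the same section it says that the levels of IL-1, IL-6, IL-8, IL-10, TNF-alfa and complements, before, during and after ECMO and in patients with sepsis, "will be determined if the investigators find relevant difference between the two groups in clinical variables".

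The Outcome Measures section carries no such condition:

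- **ECMO patients, primary outcome:** "Level of pro- and anti-inflammatory cytokines (IL-1, IL-6, IL-8, IL-10, tumor necrosis factor-alfa) before initiation of ECMO", then 2 hours after initiation, at explantation, and 6, 12 and 24 hours after explantation.
- **Septic shock, first listed outcome:** "Level of procalcitonin, Level of C-reactive protein, Level of interleukin-1", followed by IL-6, IL-8, IL-10 and TNF-alfa, at 24 and 48 hours.
- **Septic shock, Secondary Outcome Measures:** serum IL-6, described as "Comparison to enrollment or between 3 groups at 48, 72 h", and IL-1 beta and IL-10 at 24, 48 and 72 hours.

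The Study Design section declares the trial open label. The section on Statistical studies names tests but does not define a relevant difference. Complements appear in no outcome list.

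**The concern.** One part of the plan says the cytokines are measured only if something else is found first. Another part makes those cytokines the only primary outcome listed for ECMO patients. Staff who follow section 4 could properly leave the primary outcome unassayed, and the trial would then have no answer to its main ECMO question. If the assays are run, they are run because investigators who knew the allocation judged that the groups differed clinically. The cytokine comparison would then not be an analysis fixed in advance. Part of the loss could be permanent, because a value from before ECMO cannot be recovered if the sample was never drawn or kept.

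**Working it through.** The plan gives no figure on this point, so there is nothing to reproduce. The check sets the texts side by side.

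**1. Which outcomes fall under the condition?**

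| Outcome list | Under the section 4 condition | Not under it |
|---|---|---|
| ECMO primary | IL-1, IL-6, IL-8, IL-10, TNF-alfa (all of it) | none |
| Septic shock, first outcome | IL-1, IL-6, IL-8, IL-10, TNF-alfa | procalcitonin, CRP |
| Septic shock, secondary | IL-6, IL-1 beta, IL-10 | CRP, white cells, procalcitonin |
| No outcome list | complements | |

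The ECMO primary outcome is fully exposed. The septic outcomes are exposed in part.

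**2. When do the texts conflict?**

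- *Condition not met:* section 4 means no assay and the outcome lists mean assay. Both cannot be followed.
- *Condition met:* both lead to assays, but only after an unblinded judgement on clinical results.
- *Condition met after some patients have been treated:* those patients have no value from before ECMO unless samples were kept. Nothing in the available text says they are.

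**3. Can the condition be applied as written?** It would need a variable, a threshold, a decision time and a pair of arms. None is given. Two groups are named where three are randomised, so three pairs are possible. The time is open too: the Project implementation plan places the study of clinical results inside a 36-month recruitment period, with reports each year and analysis in 2023.

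**4. Can the harm be sized?** Only by inventing a rule.

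*How often assays go unrun.* Suppose that relevant meant p < 0.05 on at least one of k independent variables, with no true clinical effect. The assays are then not triggered with probability 0.95^k, which is 0.95 for k = 1 and 0.60 for k = 10. The answer follows the invented k.

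*False-positive rate when assays are run.* Assume one clinical test and one cytokine test, each two-sided at 5%. The clinical statistic is Z1 ~ N(δ, 1) with δ = d√(n/2), the cytokine statistic is Z2 ~ N(0, 1), and their correlation is ρ. The rate is P(|Z1| > 1.96 and |Z2| > 1.96) / P(|Z1| > 1.96).

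| Clinical effect d, n per arm | δ | ρ = 0.3 | ρ = 0.5 | ρ = 0.7 |
|---|---|---|---|---|
| 0 | 0 | 9.8% | 18.5% | 33.1% |
| 0.5 SD, 15 | 1.37 | 5.7% | 7.0% | 8.4% |
| 0.5 SD, 30 | 1.94 | 5.0% | 5.1% | 5.1% |
| 0.8 SD, 30 | 3.10 | 4.7% | 4.3% | 3.6% |

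For example, at d = 0.5, n = 15 and ρ = 0.5 the ratio is 0.0193 / 0.2778 = 7.0%. The unconditional rate cannot exceed 5%, because the joint probability is at most P(|Z2| > 1.96) = 0.05.

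**The case against.** The strongest reply is that the sentence in section 4 is a slip. It may be a loose translation, for instance of a word meaning whether. The mention of two groups, and of rejection and perioperative events close by, suggests text carried over from another design. The dedicated Outcome Measures section has fixed sampling times and could be taken as the operative text. This is plausible and makes the practical risk uncertain. It does not remove the conflict: the sentence is in the current text, it sits in the section that says what investigators will do, and nothing ranks one section above the other.

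A second reply is that samples are drawn from everyone and only the assay is deferred. The plan does not say so, and the primary outcome would still go unassayed if the condition were not met.

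Three stronger readings are tempting, and the documents do not support them:

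- *The condition can work only on stored samples.* The judgement is undated, so a look at early patients could start fresh sampling in later ones. The early patients would still lack baseline values, but stored samples are not the only route.
- *The false-positive rate among trials that run the assays rises above 5%.* As the table shows, that depends on the clinical effect: marked inflation with none, about 5% at 0.5 SD with 30 per arm, and less than 5% at 0.8 SD.
- *A stated share of such trials would leave the assays unrun.* Any such figure rests on a rule that the plan does not contain.

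**Conclusion.** The point holds as a direct contradiction in the current text over whether the ECMO primary outcome, and the interleukin and TNF part of the septic outcomes, will be measured at all. It must be fixed, because section 4 followed as written can defeat the primary outcome. This is a wrong rule and more than missing detail. The conclusion rests on the wording alone and needs no assumption about effect size, error rate or correlation. The size of the harm cannot be derived from the documents. The conflict shows that the primary outcome may go unmeasured. It does not show that it will.

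**What to change.** Delete the condition in section 4 and replace it with wording such as:

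> The cytokines listed as outcomes are sampled and assayed in all three groups at the times given under Outcome Measures, in every randomised patient alive and available at the sampling time, regardless of clinical results. If assays are batched, all samples are stored and all are assayed.

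The phrase on patients alive and available is needed because the plan itself expects deaths on support ("Death under ventilation and/or ECMO will be analyzed as a competing event").

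Two details should be settled in the same edit:

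- **Baseline in septic patients.** The septic lists compare with enrolment but name no enrolment sample for the cytokines. Section 4 can be read as giving septic patients a sample before treatment. Keep it and name it, so that the comparison has a baseline.
- **Complements.** If the condition is kept at all, limit it to complements, which are in no outcome list.

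The cost is a few sentences. The downside is that assay costs arise whatever the clinical results, but the outcome lists already commit to these assays. The available text gives only overall funding, so the assay cost cannot be checked.

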### Study Design

Study Type: Interventional (Clinical Trial)

Estimated Enrollment: 90 Participants

Allocation: randomized

Interventional Model: Parallel assignment

Masking: None (Open Label)

Experimental (subgroups)	Intervention / treatment (device)
Cytokine adsorber filter will be installed into the (hemodialysis or cardiopulmonary bypass (CPB) (15 patients on ECMO)	Cytokine adsorber is a biocompatible, high adsorptive polymer indicated in conditions where cytokine levels are extremely elevated.
Cytokine adsorber filter will be installed into the (hemodialysis or cardiopulmonary bypass (CPB) (15 patients with sepsis)	Cytokine adsorber is a biocompatible, high adsorptive polymer indicated in conditions where cytokine levels are extremely elevated.
Extracorporeal hemoperfusion cartridge will be installed into the (hemodialysis or cardiopulmonary bypass (CPB) (15 patients on ECMO)	Extracorporeal hemoperfusion cartridge is a biocompatible, high adsorptive polymer indicated in conditions where cytokine levels are extremely elevated.
Extracorporeal hemoperfusion cartridge will be installed into the (hemodialysis or cardiopulmonary bypass (CPB) (15 patients with sepsis)	Extracorporeal hemoperfusion cartridge is a biocompatible, high adsorptive polymer indicated in conditions where cytokine levels are extremely elevated.
Control (subgroups)	
No filter will be installed into the ECMO in	

this study group (15 patients)	
No filter will be installed into the patient with sepsis (15 patients)	

